## Research Strategy **Significance**

The ability to perform physical activity unhindered by pain is a key component of a person's quality of life. It is estimated that 10 million Americans suffer from knee osteoarthritis (OA), and for those aged 64 and older, as many as 1 in 10 have knee OA. With attendant near-crippling pain and activity restriction, OA is an important disease requiring intervention. Total knee replacement (TKR) is regarded as a safe, cost-effective treatment for OA, providing substantial improvements in functional status and quality of life, with about 85% of patients reporting satisfaction. However, for the 15% of patients dissatisfied after TKR (75,000/yr), persistent postsurgical pain (PPP) of the operated knee is their most frequent complaint. Whereas most patients experience pain relief within 6-12 weeks (wks) after TKR, about 13-20% report knee pain lasting more than 3 months (mo), despite radiological indicators of surgical success. In addition, approximately 10% of TKR patients do not show improvement in functional status and consequently suffer from depression and reduced quality of life. Limitations on physical activity by PPP interferes with performance and enjoyment of social, work, and family pursuits, thereby reducing quality of life. With more than 500,000 TKR surgeries performed in 2007, and projections estimated to be 3.48 million annually by 2030, a half million patients/yr in the USA could develop PPP of the knee. The resulting decreased quality of life and the consequent increased utilization of medical services to manage PPP thus poses a significant public health problem for our aging population.

**Chronic pain after surgery is in general a largely under-recognized clinical problem**, with an incidence of 10-50%, depending on the surgical procedure. So alarming is this problem that the FDA embarked on an ACTION (Analgesic Clinical Trial Innovations, Opportunities and Network) initiative workshop, for the prevention of PPP in September of 2009. In our own basic study of surgical trauma in a thoracotomy model, we and others have demonstrated that 50% of rats developed mechanical allodynia after 6 wk, which corresponds with the chronic post-thoracotomy pain syndrome in patients, interfering with normal daily life. Unfortunately, the efficacy of existing treatments is limited and many patients remain refractory to currently available therapies. For these reasons the development of new interventions that prevent PPP will have a major impact on public health. To formulate a successful preventive strategy, initial clinical studies need to assess the risk factors and pathogenic mechanisms underlying the development of PPP. Recent research has implicated a number of risk factors ranging from preoperative pain sensitivity and psychosocial factors, to surgical variables and greater acute postoperative pain intensity. While offering promising avenues of inquiry, no definitive risk factors have been identified.

What is known, judging from other attempts to develop models of the transition from acute to chronic pain is that the development of PPP *cannot be universally attributed to a single factor*, and that neurophysiologic and psychosocial factors all play important but varying roles. To date, however, most studies of PPP in general, or knee pain following TKR in particular, have examined the role of risk factors in isolation and/or within a single domain; a shortcoming that we believe has contributed to the paucity of consistent predictors and mechanisms and thereby undermined efforts to understand how PPP develops.

***We submit that any strategy used to investigate risk factors for PPP must not only consider multiple risk factors across various domains, but must also examine how these risk factors inter-relate, interact and combine over time to predict and/or influence the incidence of PPP following surgery.*** Doing so would greatly facilitate the development of predictive models for PPP after surgery, improve the capacity to identify patients during the preoperative period who are at highest risk, and thus promote work on interventions to prevent this chronic condition. Our proposed study will undertake such a multi-factorial prospective approach.

**Risk Factors for PPP:** Preoperative pain intensity has been implicated as a possible factor for PPP after TKR in some studies. These studies utilized validated patient measures of pain such as the numerical rating scale of pain intensity, Short Form 36 health survey, Western Ontario and McMaster Universities Osteoarthritis Index, and Knee Society Score. Recent studies have used experimental pain stimuli (e.g. heat) to quantify pain sensitivity and to predict acute postoperative pain. *The value of preoperative pain sensitivity in predicting outcomes will be enhanced in our proposed study by including both self-report of knee pain and sensitivity to experimental pain.* To our knowledge, no published studies have used a multi-domain approach to quantify pain intensity and sensitivity prior to TKR. The significance of our project will be increased by our ability to examine the degree to which pain sensitivity to experimental pain stimuli – distinct from patient self-report of perceived knee pain – predicts the incidence of PPP 6-mo post-TKR.

Preoperative levels of depressed mood and anxiety have been linked to PPP at 1 yr after TKR. Pain anxiety and pain catastrophizing are also implicated in the development of PPP after surgery. Pain anxiety is defined as the tendency to have fear-like symptoms when pain is anticipated or experienced. A crucial component of the pain anxiety construct for the proposed study is “behavioral avoidance.” This component describes the tendency to avoid movement because of fear of pain due to movement. Patients scoring high on behavioral avoidance may tend to restrict movement of their operated knees, leading to poor range of motion and PPP. Pain catastrophizing is defined as the tendency to magnify and ruminate on the most negative aspects of pain. High pain catastrophizers tend to report higher pain intensity because they focus considerably more attention on how awful the pain may be. The mechanism by which catastrophizing is thought to impact the experience of pain is by promoting sensitization or interfering with pain inhibition in the central nervous system. In OA patients, catastrophizing has been associated with high pain intensity and hyperalgesia (to electrical stimulation). Studies have shown that preoperative pain catastrophizing was predictive of PPP after TKR.

Surgical trauma induces neuroplastic changes in pain sensitivity, so that mechanical hyperalgesia can be demonstrated in both the area of inflammation (primary hyperalgesia) and in the non-inflamed surrounding tissue (secondary hyperalgesia). Primary hyperalgesia depends mainly on sensitization of peripheral nociceptors while secondary mechanical hyperalgesia occurs as a result of central sensitization in the spinal cord. Central sensitization is thought to be triggered by C-fibre nociceptive input, with activation of NMDA receptors in the spinal dorsal horn. Once central sensitization is established, dorsal horn nociceptive neurons become sensitized to previous sub-threshold stimuli and input from low threshold mechanically sensitive fibers (A- $\beta$ ). This process is accompanied by a spread of sensitivity well beyond the peripheral site of injury, termed secondary hyperalgesia. Recent studies have employed a technique to measure the *area of punctate mechanical hyperalgesia* surrounding thoraco-abdominal surgical wounds. We propose to use punctate mechanical testing in the area around the knee to assess the development of secondary hyperalgesia after TKR. In neuropathic pain conditions, it is hypothesized that central sensitization and secondary hyperalgesia persist over time so that a chronic pain state is established, and the same sequence of events most probably contributes to PPP after TKR. Moreover, it is important to note that the significance of studying the area of punctate mechanical hyperalgesia surrounding the surgical wound goes beyond basic understanding of a mechanism contributing to PPP. Unlike other potential neurobiological mechanisms (e.g. cytokines), the procedure for assessing secondary hyperalgesia can be swiftly implemented by personnel in clinical settings at a low cost (although some training is required). Thus, our proposal gains significance with regard to actual clinical practice and treatment decision-making insofar as this potential neurophysiological risk factor – secondary hyperalgesia – can be readily and frequently measured by the practitioners administering care to the TKR patient.

**Multi-Factorial Approach:** Prior literature indicates that the above described risk factors may be predictive of PPP development, but most studies considered factors one at a time. Although possible mechanisms by which psychosocial risk factors influence chronic pain severity have been offered, no TKR studies have advanced models to explain, by what mechanisms, these factors exert effects on the development of PPP over time. *Much of the significance of our proposed project in extending our understanding of PPP rests on testing prospective models that link neurophysiologic and psychosocial factors.* To this end, we propose a series of mediation models that cross these domains, and which are centered on secondary hyperalgesia as the chief neurophysiologic mechanism. Mediation models will allow us to partition the change within and across these factors so as to reveal a true (often masked) effect of the underlying mechanism.

Using pain catastrophizing as an example, we expect that this factor (assessed pre-surgery) not only exerts a significant “direct effect” on incidence of PPP at 6 mo, but also has an “indirect effect” on PPP development through its effect on secondary hyperalgesia. The “direct effect” is the kind of effect typically reported that takes into account only the observed independent association of pain catastrophizing with PPP development, but doesn’t reveal what actually translates a patient’s tendency to view pain as awful and terrible into later chronic pain. We hypothesize that high pain catastrophizers experience heightened central nervous system sensitization post-surgery, manifested as greater secondary hyperalgesia, which then lead to development of PPP over the ensuing weeks. *The significance of this project is magnified by explicit testing of these multi-factorial conceptual models that allow us to uncover the full array of multiple inter-related causal pathways in what have heretofore remained partial single risk-factor relationships. Such discoveries will reveal a host of*

*important points of intervention.* For instance, high pain catastrophizers identified at pre-surgery may not only be appropriate for specific psychological interventions, but may also be appropriate for pharmacological treatments targeting secondary hyperalgesia.

Results on whether age is a significant predictor of PPP after TKR have been conflicting. The effect of age on PPP may be more complex, because age can influence both the psychosocial and neurophysiological mechanisms for development of PPP. Therefore, in our study, age will be evaluated in mediation models in addition to being used as a moderator. One caveat about age in all of our models is that there can be age-related changes in the nociceptive system and so the neurophysiological assessment tools may be age biased. Nevertheless, the prediction models remain valid but interpretation of the mechanisms may need further refinement.

The significance of this project is further amplified by consideration of functional and quality of life outcomes following TKR. Pain level and level of physical activity are not synonymous, and represent two important determinants of quality of life. We expect that preoperative pain sensitivity and psychosocial factors, and post-operative hyperalgesia will also be associated with decreased mobility and poorer quality of life at 6-mo post-TKR. These direct and independent effects may be further mediated by PPP at 6-mo. The ability to predict knee-related physical activity restrictions from preoperative or immediate postoperative factors will allow early implementation of effective targeted interventions prior to development of a PPP syndrome. In our recent randomized, controlled, clinical trial of 240 TKR patients with perioperative pregabalin administration, we demonstrated decreased neuropathic pain and improved knee function (rising from bed, bending to floor, etc.) at 6 mo compared to the placebo group.

**Implications for Clinical Practice:** Patients who develop PPP after TKR suffer substantial loss of function and productivity in society. In addition to increasing costs of healthcare, these patients consult multiple physicians and require additional diagnostic and treatment modalities. If the incidence of PPP post-TKR (13-20% of patients) can be drastically reduced, the economic, quality of life and mobility benefits promised by TKR for the OA sufferer will be fully realized. At present, given the limited research on factors underlying transitions from acute to chronic pain, standardized and effective algorithms to guide clinical decisions are precluded. The multi-factorial and prospective approach to uncovering risk factors we propose in this application seems an appropriate and necessary step in understanding the complex phenomenon of PPP. Doing so will ultimately provide foundations upon which to develop clinical decision rules and interventions. Variables such as pain intensity and patients' cognitive/affective state are modifiable through cognitive-behavioral therapies. Also, the area of postoperative secondary hyperalgesia has been shown to be reduced by NMDA antagonists. *Explicitly addressing multi-variable, cross-domain models of modifiable risk factors will allow identification of a number of possible intervention targets.* A structured prospective clinical evaluation to determine the relative risk of each of these modifiable factors will enable physicians and patients to determine the relative risk of developing PPP after TKR and the risk/benefit of this *elective* surgical procedure and the long-term outcome.

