## Approach

**Overall Strategy:** The primary aim of this application is to investigate relationships of risk factors to the development of PPP at 6 mo following TKR, through independently predictive and mediated models. These risk factors are preoperative thermal pain sensitivity, pain anxiety and catastrophizing; postoperative area of secondary mechanical hyperalgesia or hypoalgesia (numbness) and pain intensity. **PPP** for this study will be defined as "**pain in the operated knee at six months after TKR, with other causes of pain excluded and reported intensity on 0-10 NRS scale of  $\geq 4$ .**" The study will also evaluate the relationship of PPP incidence with the severity of functional impairment. This is a single-site prospective clinical investigation of 300 consented OA patients undergoing primary, unilateral TKR. Although we realize the importance of genetic susceptibility on the development of PPP, the complexity of determining the multiple genes that may contribute to this condition is beyond the scope of this proposal. However, prior to surgery we will obtain a blood sample (8.5 mL) from all patients, process it for DNA analysis, and store at -80° C for future studies by [name], NINR (letter of support) to screen for genetic predictors of PPP, such as COMT and GCH1. We will also obtain three blood samples (5ml each) for RNA analysis. In a previous IRB approved study, we also obtained blood samples for RNA analysis prior to hip replacement surgery and 24 hours afterward and found that IL18R1 was up-regulated while IL-8RB was down-regulated and may be related to the normal acute post

operative inflammation. However, we now need to examine the changes in cytokine gene expression in the TKR patients. All of the blood samples will be sent for analysis to [name] laboratory. The patients' genetic information will stay confidential, and will be identified by a study number, and not a name. This information will not be disclosed to any other third party. Personal data will be stored at Rush University Medical Center. The samples sent to [name] laboratory will be appropriately coded so that the patient's name does not appear on the samples. Data will be kept for 1 year from the time the last patient is enrolled in the study.

Study Calendar	Preop	Post-Incision				Post-operative			
		24h	36h	48h	72h	3 wk	6 wk	3 mo	6 mo
General Physical Examination	X					X	X	X	X

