The standard ASA monitors will be placed. Written standard instructions will be given to the anesthesiologist assigned to provide intraoperative care of these patients, who will be one of the members of the orthopedic anesthesia section, of which the PI is the director. Epidural anesthesia will be induced with titration of 2.0% lidocaine (10-20 mL) with epinephrine (1:200,000). Prior to commencing surgery, a dermatomal sensory and motor level will be obtained. Patients will be sedated with propofol titrated to effect at a rate of 20-50 µg/kg/min. They will be maintained normothermic with fluid warmer and active heating devices. In addition, hemodynamic parameters will be titrated to maintain mean blood pressure within 20-30% of baseline hemodynamic status (and not below 60 mmHg mean blood pressure). All intraoperative variables such as heart rate, blood pressure, O2 saturation and temperature, intraoperative local anesthetics, sedative drugs used, amount of fluid given, blood loss, duration of surgery and tourniquet time will be documented. Once the surgery is completed, patients will be transported to the recovery room.

**Standard TKR:** Skin incision will be considered time zero; and the length of incision will be recorded. TKR will be performed under tourniquet control, using an abbreviated medial parapatellar approach with the arthrotomy extending into the quadriceps tendon for 2-4 cm above the superior pole of the patella, and without patellar eversion. A primary, cruciate retaining tricompartmental TKR will be performed in all cases (NexGen CR, Zimmer, Warsaw, IN®); all components will be cemented and the patella will be resurfaced. No local anesthetic will be infiltrated at closure of the surgical wound. The knee will be closed in 90 deg of flexion over a drain. Any intraoperative complications, especially nerve trauma, will be recorded.

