#### Acute Postoperative Assessments (total time approximately 30 min):

**(1) Pain Intensity:** The 11-point NRS pain intensity will be recorded every 4h for 0-72h postoperatively of the operated knee, then twice daily thereafter until discharge. The area-under-curve (AUC) for NRS over 0-72h will be calculated and interpreted as the burden of acute postoperative pain.

**(2) Neurophysiologic Assessment of mechanical (punctate) hyperalgesia and hypoalgesia** will be performed at least 6 hours after removal of epidural, post-incision by the RN under the supervision of PI. The elasticized (ACE) wrap around the knee will have already been removed at 24h post-incision. With the subject in a relaxed supine position with eyes closed, stimulation with a hand-held von Frey filament (4 g) will begin on the lateral aspect of the knee where the patient reports no pain sensation (Figure below), and move in 2 cm steps toward the incision until the subject reports a distinct change in sensation. The first point where the subject reports the sensation as 'painful', 'sore', or 'sharper', will be marked with an alcohol pen. To map the area of this mechanical sensitivity around the knee, testing will be done every 2.5 cm around the mid-line along radial lines. If no change in sensation is found, stimulation will be stopped at 5 cm from the surgical incision to restrict our testing to the area of **secondary mechanical hyperalgesia**. Any areas of numbness will also be noted. To quantify the area, a transparent plastic sheet with pre-marked grid marks will be placed over the knee to facilitate the transfer of the skin markings to our template. The area will then be measured with a digital planimetry software.

(a): In preliminary studies we found the mean area to be 37 cm^2. Areas of numbness will also be noted.

**(3) Functional Measures (ROM only):** The active and passive ROM of the knee will be recorded every day in the hospital by the physical therapist. In addition, the RN will measure active and passive ROM at least 6 hours

after removal of epidural, (performed at the same time as assessment of mechanical (punctate) hyperalgesia and hypoalgesia.

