**Covariates:** Preoperative covariates included are as follows: age, weight/BMI, OA severity and ASA status. Perioperative covariates include: postoperative analgesic consumption and duration of surgery. Complications after TKR will be recorded and included as a summed incidence. Patient questionnaires of drug use in the first three wks postoperatively will be converted to daily morphine equivalents and included as a covariate in the predictive models. Although the protocol stipulates uniformity in medication use during the acute postoperative period, once the patient leaves the hospital, their analgesic use over the next 6 mo cannot be rigidly controlled. To reduce variation we will prescribe analgesics as needed (per protocol above mentioned) and will remain in contact with the patients to record additional medication.

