### **Detailed Analyses:**

**Primary Aims:** are to investigate the relationships of *risk factors* and the development of PPP at 6 mo post-TKR, through independently predictive (for clinical prediction models, Hypothesis 1) and mediated models (to reveal underlying mechanisms, Hypothesis 2). These risk factors are preop thermal pain sensitivity; anxiety and catastrophizing; postop area of secondary mechanical hyperalgesia and pain intensity.

A. **Independent Risk Factors:** Risk factors will be individually predictive of the PPP (primary endpoint):

*Hypothesis 1 is that greater (↑) preop pain sensitivity, higher levels of preop pain anxiety and catastrophizing, larger areas of secondary hyperalgesia post-TKR and higher postop pain intensity will independently predict increased incidence of PPP at 6 months post-TKR.*

- 1) **Pain Intensity:** Expected Result: (Hypothesis 1): Higher postop pain intensity (↑), will independently predict increased incidence of PPP at 6 mo post-TKR (ex. ↑ postop NRS → ↑ PPP incidence).
- 2) **Neurophysiologic:** Expected Result: (Hypothesis 1): Greater preop pain sensitivity (↑) and larger areas of secondary hyperalgesia ( $\text{cm}^2$ ) post-TKR will independently predict increased incidence of PPP at 6 mo post-TKR (ex. ↑ preop thermal pain sensitivity → ↑ PPP incidence).
- 3) **Psychosocial:** Expected result: (Hypothesis 1): is that greater (↑) catastrophizing (PCS score) will independently predict increased incidence of PPP at 6 months post-TKR (ex. ↑ PCS score → ↑ PPP).
- 4) **Demographics:** Expected result: Patients 65-85 yrs will have a lower incidence of PPP than patients 18-64 yrs.

B. **Mediation Models:** Effects of preoperative factors on development of PPP occur through interrelated neurophysiologic mechanisms:

*Hypothesis 2 is that the effects of preoperative factors on development of PPP occur through interrelated neurophysiologic mechanisms. Thus, it is expected that the area of secondary hyperalgesia post-TKR will mediate links between preoperative pain sensitivity and PPP incidence, as well as mediate links between pain anxiety/catastrophizing and PPP incidence at 6 mo after TKR.*

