#### Potential Difficulties and Limitations

1. We have no way of directly assessing minor nerve damage following TKR.
2. Patient may decide to undergo another elective joint replacement procedure during the 6-mo postop period
3. Although power analysis is based on 17.8% PPP incidence, TKR procedures may vary over the 3-yr duration of study. However our power estimates are conservative and our multivariate analyses are robust and powerful.
4. 6 mo assessment of PPP can be complicated by opioid use in some patients. However, this factor is considered as a covariate in the analysis.

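### The Hypothesis 2 mediation models are given a causal reading, but nothing in the plan addresses unmeasured common causes of hyperalgesia area and PPP, such as minor nerve damage

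*Combined protocol and SAP*

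**What the plan says.** Under Significance (Multi-Factorial Approach) the mediation models are "centered on secondary hyperalgesia as the chief neurophysiologic mechanism", and testing them is said to be a step "that allow us to uncover the full array of multiple inter-related causal pathways". Detailed Analyses makes this a primary-aim hypothesis: "it is expected that the area of secondary hyperalgesia post-TKR will mediate links between preoperative pain sensitivity and PPP incidence", with a parallel statement for pain anxiety and catastrophizing.

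General statistical analysis plans the causal-steps method with bootstrap intervals, plus Sobel tests and R-squared effect sizes. Detailed Analyses also expects the mediated model to fit better than the direct one.

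Potential Difficulties and Limitations says: "We have no way of directly assessing minor nerve damage following TKR". It draws no consequence for Hypothesis 2.

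Some nerve-related information is collected:
- Standard TKR: "Any intraoperative complications, especially nerve trauma, will be recorded".
- Acute Postoperative Assessments, at the visit that maps hyperalgesia: "Any areas of numbness will also be noted".
- Overall Strategy lists among the risk factors "postoperative area of secondary mechanical hyperalgesia or hypoalgesia (numbness) and pain intensity". The list in Detailed Analyses drops hypoalgesia.
- The neuropathic pain examination (StEP) is done before surgery and at 6 months, and serves as a secondary endpoint.

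Covariates has no nerve-injury term. Its only complication term is: "Complications after TKR will be recorded and included as a summed incidence".

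**The concern.** The indirect effect is the product of two paths: preoperative factor to area, and area to PPP. Neither the factor nor area is randomised. Even if the first path is sound, the second is causal only if nothing unmeasured drives both area and PPP. Nerve damage at surgery is an obvious candidate, since it could alter sensation around the knee and also cause lasting pain by another route.

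The planned tools quantify sampling error and effect size from the observed variables. Resampling confounded data gives an interval around a confounded value, so none of them would give a warning.

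At stake is the reading of a primary-aim result. The Multi-Factorial Approach section suggests that high catastrophizers may be suited to drug treatment aimed at hyperalgesia. If area were only a marker of nerve damage, later work could be directed at the wrong target.

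**Working it through.** **Inputs from the plan.** PPP incidence is 17.8% (46/259 = 0.178, reproduced). Analysable patients: 300 × (1 − 0.15) = 255, so about 255 × 0.178 = 45 PPP events. The plan gives no power or effect size for Hypothesis 2, so there is no mediation figure to reproduce.

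**Assumed, not in the documents.** Path from preoperative factor to area a = 0.3 SD per SD. Nerve damage is binary, unrelated to the preoperative factor, with prevalence p = 10–30%. It shifts area by δ SD and multiplies the odds of PPP by OR. The true effect of area on PPP is zero.

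**Step 1: size of the bias.** Omitting nerve damage leaves a alone and biases the area-to-PPP coefficient b. A rough linear approximation is

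bias in b ≈ ln(OR) × δp(1−p) / (1 + δ²p(1−p)).

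- δ = 1, p = 0.2, OR = 3: 1.099 × 0.16/1.16 = 0.15 log-odds (simulated: about 0.17).
- δ = 1, p = 0.3, OR = 5: 1.609 × 0.21/1.21 = 0.28 (simulated: 0.31).

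The sign follows δ. If nerve damage shrinks area and raises PPP risk, the bias is negative and works against the hypothesised mediation.

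**Step 2: why a matters.** With δ = 1 and p = 0.2, the residual SD of area is √1.16 = 1.077, so the standard error of a is about 1.077/√255 = 0.067. At a = 0.3 the first path is about 4.4 standard errors from zero and is nearly always found. The result then turns on the biased b. At a = 0 the interval for the product nearly always covers zero.

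**Step 3: simulated rate of false mediation** (linear model for area, logistic model for PPP, uncorrected 95% interval for the indirect effect, a = 0.3, prevalence 10–30%):

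| Nerve damage | Omitted | Adjusted for |
|---|---|---|
| Weak (0.5 SD, OR 2) | about 6–8% | about 5% |
| Moderate (0.8 SD, OR 3) | 9–21% | about 5% |
| Strong (1.0 SD, OR 4) | 19–45% | about 5% |

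The strong row moves by several points with simulation details, so read these as orders of size.

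**Step 4: variations.**
- a = 0: at most about 2%.
- Percentile bootstrap, 1.0 SD, OR 3, prevalence 20%: 17.9% at a = 0.2 (6.6% adjusted) and 21.5% at a = 0.3 (7.3% adjusted).
- Step-down Bonferroni, assuming three mediation tests (first step 0.05/3 = 0.017), prevalence 20%: about 8% (moderate) and 21% (strong).
- Better-fit criterion, read as a likelihood-ratio test of adding area: with a = 0 and a 1.0 SD shift, fit improves significantly in 22.6% (OR 3, prevalence 20%) to 54.7% (OR 5, prevalence 30%) of studies, against 5.9% with no nerve damage. This criterion can be met without any path from the preoperative factor.

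**The case against.** The strongest reply is that much of this is assumption. The documents give no prevalence, strength or direction for nerve damage, and no passage states an effect on PPP that bypasses area. The Significance section's account of central sensitization puts hyperalgesia on the path to chronic pain. If nerve damage acted only through area, there would be no confounding. Nerve damage might also produce numbness and a smaller hyperalgesic area. All of this stands. It limits what can be said about size and direction, but it does not supply the assumption that a causal reading needs.

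A reader might infer more than the documents support:
- **That nerve damage would be reported as mediation.** This is not automatic. The bootstrap and Sobel tests also need the preoperative factor to predict area, and weak nerve damage changes little.
- **That the plan itself names a common cause, or that nothing can be done.** The limitation says only that minor damage cannot be assessed directly. Numbness and overt nerve trauma are recorded and are partial proxies.
- **That recorded nerve trauma is lost in the complication sum.** Standard TKR speaks of intraoperative complications and Covariates of complications after TKR. The documents do not say whether the first enters the second.
- **That the plan would recommend treatment on this evidence.** It says only that such patients may be suitable, and leaves validation of the prediction equation and any trials to later studies.

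Requiring every claim to survive a fixed grid would be too harsh. In a simulation of true mediation with no nerve damage (a = 0.3; area OR 1.24^2.9 = 1.87 per SD, borrowing the plan's acute-pain effect), power was 93%. Only about 26% of studies kept the claim after a spurious OR of 1.45 was subtracted.

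**Conclusion.** The point holds in a limited form. The plan gives its mediation results a causal reading, leaves the required no-confounding assumption unstated, and has no analysis of how far the results depend on it. An omitted common cause could bias the indirect effect and be taken for mediation if the preoperative factor predicts area, which is the case the study expects. The false-mediation rate then ranges from close to nominal (weak nerve damage) to 19–45% (strong), and a multiplicity correction roughly halves the moderate and strong rates. These figures rest wholly on the assumed strengths, an assumed a = 0.3 and the assumed direction. They show that the risk is not negligible, not that it has occurred. The prediction models of Hypothesis 1 need no causal reading and are not affected by this point.

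**What to change.** In General statistical analysis and the Hypothesis 2 parts of Detailed Analyses:

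1. State that a causal reading of each indirect effect assumes no unmeasured confounding of area and PPP.
2. As a sensitivity analysis, add numbness at the mapping visit to both the area and the PPP equations, as an area if it was measured on the template and otherwise as present or absent. Add recorded intraoperative nerve trauma as its own term where it is frequent enough to estimate with about 45 events. Trauma recognised in theatre does not capture minor damage, so this step alone is not sufficient. StEP at 6 months is measured with the outcome and is a poor adjuster.
3. For each Hypothesis 2 indirect effect, report the confounder strength at which its interval reaches zero, over a stated range of prevalence, shift in area and OR, with shifts in both directions and no pass/fail rule.
4. Describe results as associations consistent with mediation, with the tipping point beside them, rather than as established causal pathways.

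The cost is SAP wording and a short added computation on data already planned, with no new visits or patients. The downside is that mediation claims will be more cautious.
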